6.1. KNOWN AND ANTICIPATED RISKS AND DISCOMFORTS

There are no known or anticipated physical, psychological, social, legal, or economic risks from taking part in this study.

Psychologically, if a participant is not comfortable answering or does not want to answer a question in the study, she does not have to answer it. When looking at summaries of de-identified data and comparing it to her own situation, it is possible that a participant may learn information that is upsetting to her.

One potential risk is a loss of private or confidential information, such as from a security breach. In the event of a breach, we will let participants know about it as soon as possible.

6.2. STEPS TAKEN TO MINIMIZE RISK

6.2.1. Data Security

While we cannot guarantee security for information stored on each participant's computer or mobile device(s), or while it is being transmitted via cell phone towers, Wi-Fi, or the Internet, once received, our database has a FISMA-moderate level of security, including multiple security safeguards and protections. To minimize the risk of a security breach, we will:

- Use up-to-date, compliant, and proven database and security software and data transmission protections (See Section 5.1 for details)
- Monitor the Website and database system continually
- Maintain updated anti-viral protections
- Conduct regular evaluations of the database and security features by an independent, outside security expert
- Maintain multiple levels of restricted access for user access (e.g., a password is needed to enter), application access (e.g., role-based access to features, access audit trails), and hosting services (e.g., firewall, secure sockets layer)
- Store direct participant identifiers (i.e., subject names and other personally identifiable information) in tables separate from medical information
- Limit access to participant identifier tables to the Coordinators only
- Anonymize any shared data following current HIPAA standards

These safety features help ensure that participant information is protected. In the event of a breach, we will notify participants about it as soon as possible.

6.2.2. Contacting Subjects about Other Clinical Studies

As mentioned in Section 4.4.5, approved researchers will not have access to personally identifiable information for any participants that would allow them to contact participants directly. Once approved, potentially eligible and interested participants would be sent the

contact information for the researchers by the Coordinators; it would be each participant's choice whether to contact those investigators.

Studies external to PregSourceSM would consent participants separately, based on each study's IRB requirements.

6.2.3. Sharing De-identified Data with Other Researchers and/or Data Repositories

Researchers may request de-identified data from the study to analyze for research purposes, such as to estimate the prevalence of clinical manifestations or numbers of participants who may be eligible for approved clinical studies or trials. The Operations Committee or its designees will review these requests. If approved, researchers may be given access to the data via the Website's Professional Portal and/or sent a file of the de-identified data.

De-identified data may also be deposited in data repositories, such as the DASH.

6.3. CLASSIFICATION OF RISK

Per 45 CFR 46, PregSourceSM falls under Subpart B, Additional Protections for Pregnant Women, Human Fetuses, and Neonates Involved in Research.

For adults, including those without consent capacity, PregSourceSM will involve only minimal risk.

For infants/children, PregSourceSM falls under 45 CFR 46.404, "Research that does not involve greater than minimal risk to children," as we will be collecting developmental data on the infants born to the mothers and reported by them.

Overall, given the known and anticipated risks and discomforts, PregSourceSM will not involve more than minimal risk to any participant, and we believe the risks are reasonable in relation to anticipated benefits.

6.4. ANTICIPATED BENEFITS

6.4.1. Direct Benefits

A participant will not benefit directly from participating in PregSourceSM.

6.4.2. Indirect Benefits

Because PregSourceSM provides a means for each participant to track her personal health information, and it may suggest that she contact her healthcare team based on her answers to particular questions, it may help her better inform her healthcare team about her health. For example, if a woman indicates that she is gaining weight beyond recommended levels, the database may send her a message telling her that she may want to discuss this with her prenatal care provider. Both the tracking capabilities and the prompts may help her healthcare team better monitor and address her healthcare needs.

Each participant will also get evidence-based information about pregnancy. For example, if a woman indicates that she has morning sickness, she will be able to see how many other women in the database also have this symptom. She will also get links to information and websites about morning sickness from PregSourceSM partner organizations and other trusted sources.

Finally, being able to see how she compares to others similar to her may give a participant some peace of mind about her concerns (i.e., “I’m not the only one”) and/or prompt her to contact her healthcare team for issues that are of concern (i.e., “This doesn’t seem normal – I should see my doctor”).

SECTION 7. SUBJECT SAFETY MONITORING

7.1. STUDY MONITORING PLAN

7.1.1. Data and Safety Monitoring Plan and Stopping Rules

7.1.1.1. Safety

Because we do not anticipate any health risks to participants for taking part in PregSourceSM, we will not have a Data and Safety Monitoring Committee. The lead principal investigator, in conjunction with the Management Team, will monitor study data and safety.

PregSourceSM, its Website, and app content are not intended to be a substitute for independent, professional medical judgment, advice, diagnosis, or treatment. Participants should always seek the advice of their physicians or other qualified health providers with any questions or concerns they may have regarding their health, their pregnancy, or their baby's health.

If a participant reports a health- or safety-related concern, the Coordinator will report it to the lead principal investigator and the Management Team for review.

If a participant enters data indicating a health or safety concern, the database will send an automated notice to her that she may want to contact her doctor for advice. The database may also refer her to related factsheets and websites with further information.

7.1.1.2. Futility and Stopping Rules

The Operations Committee will review study recruitment numbers and study data completion rates annually. If recruitment targets and/or study questionnaire completion rates are not within the expected target, the Committee may recommend options to the Director of NICHD to alter the design, halt, or terminate the study.

If a particular study question or questionnaire is being completed by less than 67% of relevant participants, the Committee will review it and may recommend revisions and/or deletions.

7.1.2. Procedures for Suspending or Stopping Enrollment

PregSourceSM will suspend registration and data entry if there is a security breach that compromises the ability to collect information in a secure, confidential manner. Participants will be notified in a timely manner about the breach. Registration/data entry will be restarted only if/when the Management Team, including the independent security experts, are confident that the system is secure, and the IRB has approved continuation.

If the study end is planned for a set future date (e.g., at the end of the contract), new participants will be warned of the end date before they join, so that they may make an informed decision about whether to enroll.

When PregSourceSM ends, current participants will be notified of the end date and given a reasonable opportunity (e.g., 3 months) to download and/or print their own data before the Website and database are shut down.

7.2. QUALITY ASSURANCE

7.2.1. Data Curation

PregSourceSM Coordinators will be trained in curation methods to review and investigate participant responses, reports, or registration details that are inconsistent with each other and/or the expected clinical course or status of the participant. Coordinators will follow up with the participant, as needed, to correct and/ or explain the inconsistencies.

7.2.2. Monitoring the Participant Registration Process

PregSourceSM's curation and quality monitoring program will assess the appropriateness of the participant through a review of contact, demographic, and consent details. If the participant appears valid, the PregSourceSM Coordinators may review a selection of Health History questionnaire responses. Accounts are assessed and assigned a status with regard to the completeness and reliability of the participant-provided information. Monitoring is ongoing as the participant contributes future information.

7.2.3. Monitoring Participant Burden

PregSourceSM will implement a curation and quality monitoring program to monitor participant burden of use and adherence/attrition over time. This will include monitoring:

[figure not shown]
- Number of participants who complete monthly questionnaires
- Number of participants who complete weekly trackers at least once per week
- Number of participants who have turned off/adjusted reminder frequencies in their Profiles
- Number of participants who dropout (do not enter data for more than 3 months) and/or withdraw from the study, the timing in their pregnancy of dropout/withdrawal, and their demographic characteristics
- Number of participants continuing to enter data through the end of their pregnancy
- Number of participants continuing to enter data for neonatal outcomes
- If participants enroll at earlier gestational ages, are they more or less likely to continue entering data throughout their pregnancy?
- Are participants more likely to enter certain types of data than others (morning sickness, sleep, mood)?

The database will also use statistical tracking and Google Analytics to report on participants':

- Date of registration
- Date of last login
- Date of last update (demographics and complete audit of questionnaire responses)
- Registrants by country
- Registrants by date

- Website visitors by date
- Website visitors by country
- Most frequently accessed content
- Average length of time spent on the site
- Number of app downloads

For example, the system can report on completion of health history questionnaires similar to the pie chart or bar chart below. Additional sample reports can be viewed at <http://www.nltechno.com/awstats/awstats.pl?config=destailleur.fr>.

We will also be monitoring site/app usage statistics and analyzing user behaviors so we can refine questions and site/app function as PregSourceSM continues. For instance, if the majority of users drop out of the pre-conception survey before completing it, we can break up the survey into segments to make it easier for people to complete.

7.2.4. Monitoring Recruitment and Demographic Distribution

PregSourceSM coordinators will monitor recruitment every quarter – and more often if necessary – paying particular attention to the demographics (race, ethnicity, income) of U.S. participants in the study population. If minority enrollment is more than ~10% below the demographics of the U.S. population, based on the most recent U.S. Census for which data are publicly available, the Operations Committee will initiate additional recruitment efforts to enroll participants from under-represented sub-groups.

7.2.5. Lost to Follow-up

Because the pregnant woman will be the person entering data, and given the possibility of maternal deaths, we will give the participant the option of providing the name and email address for an alternate contact (e.g., a family member or friend). If the participant has not entered final maternal and neonatal outcome data after repeated reminders, at 6 months after her expected due date, the Coordinators will email the alternate contact to try to gather this information if permission is granted under Contact and Sharing Preferences.

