In 2009, the U.S. Centers for Disease Control and Prevention (CDC) reported an estimated 6,369,000 pregnancies – 102 pregnancies per 1,000 women – resulting in 4,131,000 live births and 1,087,000 fetal losses (Curtin SC, et al 2013). While many of these women are seen by physicians, and hundreds of research studies are conducted, we know more about pregnancy complications, than about the natural history of human pregnancy. There is limited to no information on normal pregnancy despite its prevalence as the majority of studies are performed on specific conditions. Furthermore, even those tend to be case series and not representative of the population. In a review of clinicaltrials.gov there are no ongoing studies characterizing normal pregnancy. Information collected in any systematic way from the patient's point of view about how pregnancy affects the lives of women in our modern world is also missing, such as:

- How many women get morning sickness? How long does it generally last? At what gestational ages does it tend to occur? Does it have any impact on maternal weight?
- How does being pregnant affect women's sleep, energy levels, and mood? How do these change over the course of the pregnancy?
- What is the impact of pregnancy and pregnancy symptoms on women's lives? How easy is it to stick to your doctor's orders for diet, exercise, and special treatments?
- How is being pregnant more challenging for certain women (e.g., women with physical and intellectual disabilities)?

We believe that PregSourceSM: Crowdsourcing to Understand Pregnancy (PregSourceSM) will help us gather information directly from pregnant women as they experience it, so that we can help answer some of these questions. According to Project HealthDesign, "Lay people engage in health practices and health behaviors every day, not just during visits to clinicians. They revealed that they attend not only to signs and symptoms of illness as directed by clinicians, but also to the idiosyncratic, highly personal thoughts, behaviors, attitudes, sensations, and environmental conditions that inform them about their health state and alert them to take action related to health. These observations of daily living (ODLs) complement traditional signs and symptoms of disease (e.g., blood pressure, shortness of breath) and highlight the personal experience of health and disease (Brennan 2010)."

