4.4.2. Account Profile Set up and Health History Questionnaire

Once registered and consented, a participant can begin to enter information after reading the PregSourceSM Privacy Policy and Terms and Conditions of use, then completing her Account Profile and taking an initial Health History questionnaire to collect data on:

- Contact information and preferences (email, text, etc.), including an optional alternate contact²
- Demographics and socioeconomic -- NIH-required race/ethnicity data, general family income ranges, education levels

² Alternate Contacts will be contacted only in cases when repeated attempts to gather final pregnancy outcome information have been unsuccessful.

- Interest in participating in a clinical trial. The participant will be asked for her consent to allow the PregSourceSM coordinators to contact her regarding future opportunities for participation in a clinical trial or research study.
- Pre-pregnancy general health – height, weight, a checklist for chronic conditions (e.g., diabetes, lupus), medications
- Reproductive health – contraceptive use, previous pregnancy histories, infertility, use of assisted reproductive technologies
- Current pregnancy health – gestational age, number of fetuses, date of first prenatal visit, prenatal visits completed, any diagnoses received or test results.

A participant will access PregSourceSM questionnaires online and/or via a mobile app to enter her own data. She will be able to download apps (e.g., via the iTunes or Android online app stores) to a smartphone or tablet, and connect these to her online account.³ The apps, as well as the Website, will let her access and enter data into online surveys and trackers. A participant will also be sent reminders and push notifications, asking her to update her information.

All questionnaires will be constructed using “Smart Survey Design” – i.e., using conditional or skip logic to add or skip questions that are not relevant, based on previous answers. Aggregated data will help us analyze response frequencies for survey questions.

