4.4.2.1. Trackers

Each participant can enter data in a set of health “trackers” – online or in-app software diaries that capture daily or weekly information over the course of pregnancy about her weight, nausea symptoms, mood, and sleep. Additional trackers may be added at a later date for tracking nutrition, exercise, and pain. She can enter data in the trackers as often as she chooses. We anticipate that for trackers such as nausea, sleep, and mood, a participant might enter data on a daily basis; while weight data might be entered only once a week or even once a month. Most trackers will collect data on timing, duration, severity/intensity, and related issues. A 2013 report by Citrix⁴, a software company that tracks app usage, shows pregnancy related apps to have wider usage. Many of the available trackers have been used and/or validated in the pregnant population⁵. Recent research articles⁶ have demonstrated the use of web-based methods to collect relevant health related information from pregnant women.

Unless otherwise indicated in her Account Profile, a participant will be reminded on a weekly basis to update her information, if she has not entered new data within the past two weeks.

³ Participants will not be required to use the apps. The apps will be available as a potentially more readily available means of accessing the questionnaires and trackers.

⁴ Nick Bilton, New York Times, August 26, 2015

⁵ Hämeen-Anttila K, Nordeng H, Kokki E, Jyrkkä J, Lupattelli A, Vainio K, Enlund H. Multiple information sources and consequences of conflicting information about medicine use during pregnancy: a multinational Internet-based survey. *J Med Internet Res.* 2014 Feb 20;16(2).

⁶ Wise LA, Mikkelsen EM, Rothman KJ, Riis AH, Sørensen HT, Huybrechts KF, Hatch EE. A prospective cohort study of menstrual characteristics and time to pregnancy. *Am J Epidemiol.* 2011 Sep 15;174(6):701-9

We anticipate including the following trackers:

Weight tracker. Weight would likely be entered weekly/monthly. Data collected includes:

- Weight (in pounds or kilograms)⁷

Nausea tracker. The Nausea Tracker could be entered as often as necessary, collecting data on:

- Date
- Timing (morning, afternoon, all day)
- Duration
- Severity (just nauseous, vomited)

Sleep tracker. In addition to asking about a participant's sleep patterns and apnea diagnosis prior to pregnancy in the initial health questionnaire, the Sleep Tracker may collect data on:

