4.4.2.2. Gestational Age Questionnaires

Once a month, PregSourceSM will send each participant an email, text, or app push notification, with a link to a new questionnaire relevant to her current week of gestation. For example, at 25 weeks of gestation, we may ask whether she has felt her baby move yet. At the end of each questionnaire, if the participant has not entered data into the health trackers in the past month, she will be taken to the appropriate trackers to enter information. This process will allow PregSourceSM to reduce duplication of questions, and capture changes over time in a consistent manner (e.g., all weight data will be entered into the Weight tracker).

If a participant does not complete her monthly questionnaire, she will receive a reminder once a week to do so via email or text to review the information she has entered into the database and provide any appropriate updates to her information.

Gestational-age questionnaires will continue monthly through pregnancy and then quarterly up to 36-months post-partum to capture information on maternal recovery and neonatal and infant outcomes and development.

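### Outside tracing of a missing pregnancy outcome is tied only to the due date, and three months of silence triggers no action, so an unreported loss waits longest and is recorded as attrition

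*Protocol*

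**What the plan says.** Contact with the woman herself:

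- Section 4.4.2.1 (Trackers): unless her profile says otherwise, "a participant will be reminded on a weekly basis to update her information, if she has not entered new data within the past two weeks".
- Section 4.4.2.2 (Gestational Age Questionnaires): a questionnaire matched to her week of gestation goes out each month of pregnancy, then quarterly to 36 months post-partum. "If a participant does not complete her monthly questionnaire, she will receive a reminder once a week to do so".
- Section 4.4.4 (Follow-up): regular reminders are meant to prompt entries that include pregnancy and newborn outcomes.
- Section 7.4: she can switch reminders off in her profile.

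Contact beyond the woman:

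- Section 7.2.5 (Lost to Follow-up) starts from the case "If the participant has not entered final maternal and neonatal outcome data after repeated reminders". Then, "at 6 months after her expected due date, the Coordinators will email the alternate contact to try to gather this information", and only "if permission is granted under Contact and Sharing Preferences".
- The footnote to 4.4.2 makes this a last resort: "Alternate Contacts will be contacted only in cases when repeated attempts to gather final pregnancy outcome information have been unsuccessful". Naming such a contact is optional.

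Status of a silent or bereaved participant:

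- Section 7.2.3 lists for monitoring the "Number of participants who dropout (do not enter data for more than 3 months) and/or withdraw from the study", with timing in pregnancy and demographics. It attaches no action to an individual woman's silence.
- Section 4.4.3 ends participation at termination, miscarriage or stillbirth, unless she chooses to go on entering data through later pregnancies.

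**The concern.** Sections 4.4.2.2, 4.4.3, 7.2.3 and 7.2.5 do not join up. Participation ends at a loss, but the protocol gives no route by which the registry learns of a loss that the woman does not enter. The only outside trigger runs from the due date. It depends neither on how long she has been silent nor on when the pregnancy ended, so the earlier the pregnancy ends, the longer the wait. Meanwhile the questionnaire schedule treats her as still pregnant, and the monitoring report shows her as a dropout.

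Section 2.3 says the registry describes women's experiences and pregnancy outcomes, and 2.3.1 lists gestational age of delivery and the health of baby and mother as primary outcomes. De-identified data go to outside researchers, and summaries go to participants. If outcomes are missing more often after one kind of ending than another, later users cannot repair that from the data, because an unreported loss looks the same as any other dropout. Gestation-specific messages after a loss may also distress the woman. Section 6.1 mentions upset from viewing summary data but does not consider this.

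**Working it through.** The protocol gives no figure for completeness of outcomes or time to tracing, so there is nothing to reproduce. The delays follow from its own rules.

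Inputs from the protocol: outside tracing at due date plus 6 months (7.2.5); dropout mark at more than 3 months without data (7.2.3); monthly questionnaires in pregnancy (4.4.2.2).

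Assumptions: due date at 40 weeks; 6 months = 26 weeks; 3 months = 13 weeks; one month = 4.35 weeks; her last entry falls at about the time the pregnancy ended.

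**Step 1. Delay to outside tracing.** For a pregnancy ending at week g, delay = (40 − g) + 26 weeks. A trigger at the dropout mark would act at about 13 weeks whatever the value of g.

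| Pregnancy ends at | Delay under 7.2.5 | At the 3-month mark | Difference |
|---|---|---|---|
| 10 weeks (loss) | 30 + 26 = 56 weeks | 13 weeks | 43 weeks |
| 20 weeks (loss) | 20 + 26 = 46 weeks | 13 weeks | 33 weeks |
| 40 weeks (birth) | 0 + 26 = 26 weeks | 13 weeks | 13 weeks |

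The two triggers are different steps. Section 7.2.5 writes to a third person, whereas a message at the 3-month mark would go to the woman. The table compares when each acts.

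**Step 2. Does a different interval after the due date help?** Replace 26 by any k. A 10-week loss waits 30 + k weeks and a 40-week birth waits k weeks, so the gap stays at 30 weeks. The anchor causes the gap, not the length of the interval.

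**Step 3. Gestation-specific questionnaires after an unreported loss, up to the due date.** After a 10-week loss: 30 / 4.35 = 6.9, about 7. After a 20-week loss: 20 / 4.35 = 4.6, so 4 or 5. Each carries weekly reminders if reminders are left on. Of these, (30 − 13) / 4.35 = 3.9 and (20 − 13) / 4.35 = 1.6 fall after the 3-month mark, so a hold at that mark would stop about 4 and 1 to 2.

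**Step 4. Effect on the observed share of losses.** Let p be the true share of losses among enrolled pregnancies, and let s_L and s_B be the proportions whose outcome is never captured after a loss and after a birth. Then

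observed share = p(1 − s_L) / [p(1 − s_L) + (1 − p)(1 − s_B)].

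If s_L = s_B, this equals p and there is no bias. If s_L > s_B it lies below p, and if s_L < s_B it lies above p. The protocol gives neither s_L nor s_B, so neither sign nor size can be derived.

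**The case against.** The strongest reply is that the woman is asked early and often. Tracker reminders start after two weeks without data, missed questionnaires bring weekly reminders, and 4.4.4 includes pregnancy outcomes in the purpose of the prompts. A reader might infer from 7.2.5 that nobody seeks a missing outcome until 6 months after the due date. The documents do not support that: the delay applies only to contact beyond the participant. What remains is that the prompts are described as requests to update information or finish a questionnaire, and none is described as asking whether the pregnancy has ended.

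A reader might also infer that losses will be under-counted, perhaps by starting from the figures in Section 1, "resulting in 4,131,000 live births and 1,087,000 fetal losses", out of 6,369,000 pregnancies (1,087,000 / 6,369,000 = 17.1%). That does not follow. A late email delays ascertainment. It causes an under-count only if capture after a loss ends up poorer than after a birth, and the direction could be the reverse. The 17.1% is also a share of all national pregnancies, whereas the registry enrols women already pregnant and so misses losses before enrolment. Pregnancy-loss rate is not itself a listed outcome, and 8.1 plans no statistical analysis.

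Nor can one say that birth data generally come late from a proxy. That holds only for non-responders who named a contact and gave permission.

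Sections 7.2.1 and 7.2.2 offer some protection. Coordinators follow up inconsistent entries, and accounts receive a completeness and reliability status. But 7.2.1 concerns entries that conflict, not entries that stop, and 7.2.2 attaches no outcome enquiry to silence. Continued gestational content does require both that the loss goes unreported and that reminders stay on. This narrows the group affected but does not close the gap.

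**Conclusion.** The point holds as a gap in how outcomes are ascertained, not as a demonstrated bias. Following the protocol as written, an unreported loss waits 56 weeks (10-week loss) or 46 weeks (20-week loss) for outside tracing, against 26 weeks for a 40-week birth, and only if a contact was named and permission given. Until then it is recorded as attrition. The mark of more than 3 months without data already exists but triggers nothing, and no stop is stated for gestation-specific questionnaires.

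The delays rest on a 40-week due date and 26 weeks for 6 months. The consequence is a risk of differential under-ascertainment of pregnancy outcomes. The protocol gives no capture rates, so no percentage should be attached to it. The change is worth making because it is cheap and concerns outcomes that the registry exists to describe.

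**What to change.** In 7.2.3, 7.2.5 and 4.4.2.2:

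1. When a participant passes the existing mark of more than 3 months without data, send one neutral automated status question: still pregnant, baby born, pregnancy ended, or prefer not to say, with a date.
2. Until she answers, let that question replace the routine gestation-specific pushes and reminders. Leave the questionnaires available in her account, so that a woman who is still pregnant can complete them.
3. Store with every outcome report its source (self or proxy) and its date, so that later users can separate late proxy reports from the woman's own.

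This ties 4.4.2.2, 4.4.3, 7.2.3 and 7.2.5 together through a threshold the protocol already defines. Leave the timing of the alternate-contact email as it is. Bringing it forward would keep the due-date anchor and the 30-week gap, and would approach a relative sooner about a possible loss, which is a privacy trade-off.

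Cost: protocol wording, one automated message and two stored fields. The downside is one more message to women who have gone silent, and possibly a few gestational questionnaires lost from women who are still pregnant. Some women who ignored the weekly reminders will ignore this question too, so it reduces the gap without removing it.
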